## 9.1.1. Multiplicity Adjustment

Not applicable.

## 9.2. Statistical Analyses

The statistical analysis plan (SAP) will be finalized prior to end of trial and it will include a more technical and detailed description of the statistical analyses described in this section. This section is a summary of the planned statistical analyses of the most important endpoints including primary and key secondary endpoints.

© 2015-2021 TransCelerate BioPharma

Doc. No. CT 2.01.01. Valid from 31 Jan 2022. Only the electronic version is valid.

Page 44 of 65

The main statistical analysis is planned when

- The planned number of participants have been included
- All included participants have either finalized their last assessment or has/is withdrawn according to protocol procedures
- All data have been entered, verified and validated according to the data management plan

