# 3. Objectives, Endpoints, and Estimands

The hypothesis to be tested is superiority of Plenadren compared to thrice daily Cortisone to improve patient outcome, including:

- Improved HRQoL, including mood and cognitive function
- Improved sleep quality
- Improved working ability (i.e. less sick leave, lower frequency of sick pension)
- Improved cognitive function
- Reduction in clinical risk factors of cardiovascular and metabolic diseases including weight, waist circumference, blood pressure, lipid profile, bone health, fat distribution and glucose levels.

**Objective**: To determine whether Plenadren or conventional Cortisone is superior for improving overall patient outcome in newly-diagnosed patients with PAI.

**Primary endpoint**: Differences in health-related quality of life (HRQoL) scores in patients receiving Plenadren and conventional Cortisone at time of diagnosis and 1, 6, and 12 months after treatment-initiation in newly diagnosed patients with PAI, using two validated questionnaires: one specific for PAI (AddiQoL-30) and one generic (RAND-36).

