# 4. Study Design

# 4.1. Overall Design

This is a phase 4 RRCT designed to test if oral replacement treatment with Plenadren is superior to conventional oral treatment with Cortisone in participants with newly diagnosed PAI between 16-80 years of age. The participants are assigned to one of two treatment types in parallel for the duration of the study. The primary outcome is improvement of HRQoL. To avoid the potential bias we will only include newly diagnosed patients as these will be treatment-naïve and unable to compare with other forms of replacement therapy.

The end of the study is defined as the date of the last visit of the last participant in the study.

A participant is considered to have completed the study if the participant has completed all periods of the study including the last visit.

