### 6.4. Blinding, Masking

This is an open-label study; potential bias will be reduced by central randomization.

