### **8.2.1.** Patient Reported Outcome (PROMs)

- Two HRQoL will be sampled at baseline and after 1, 6 and 12 months; the generic questionnaire RAND-36 and the PAI-specific questionnaire AddiQoL. RAND-36 is thoroughly validated and extensively used and suitable both for comparison of HRQoL scores between PAI and healthy controls, and for comparing score between PAI and other disease groups (20). The AddiQoL is developed and thoroughly validated by us as a PAI-specific HRQoL instrument, more sensitive for detecting changes in HRQoL over time in PAI (21).
- For evaluation of sleep, Sleep Diary will be sampled at visit 5-6.
- Working ability (i.e. sick leave, sick pension) will be registered at each visit (NOKLUS study form).
- Cognitive test administration using Memoro, a web-based cognitive test platform developed by [name] and [name], NTNU (28-30). The test can be run on a computer, tablet, or smartphone. Participants receive links via sms, e-mail, as a printed pdf (letter) or through helsenorge.no. Memoro uses same encryption as online banking (nettbanken) and has ROS analysis approving the system. The server is located at NTNU's central server location. No clinical data is stored only the test scores. Some background variables are stored to provide norm data for references (year born, education level according to groups (vgs., bachelor, master or above) and handedness). Participants can receive their scores relative to the norm data if that is of interest. Score will be transferred directly to TSD or similar server at UiT/Haukeland or via encrypted file sender. The cognitive tests that will be used have been used in many other studies (incl. HUNT and MoBa) and have therefore system norms as a reference.

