## 8.9. Immunogenicity Assessments

Immunogenicity to the study drugs is not a clinical problem

© 2015-2021 TransCelerate BioPharma

Doc. No. CT 2.01.01. Valid from 31 Jan 2022. Only the electronic version is valid.

Page 41 of 65

The statistical analysis plan will be finalized prior to inclusion of the first participant and it will include a more technical and detailed description of the statistical analyses described in this section. This section is a summary of the planned statistical analyses of the most important endpoints including primary and key secondary endpoints.

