## 9.1. Statistical Hypotheses

Table 4 includes all objectives with corresponding hypothesis and statistical analyses.			
Number	Objective	Hypotheses	Statistical analysis
	Primary		
1.1	Is improvement of HRQoL in PAI patients treated with Plenadren better than improvement of HRQoL in PAI patients treated with Cortisone after 6 and 12 months?	Null hypothesis:  H 0 : $P_{Plen(0-12)} = P_{Cort(0-12)}$ Alternative hypothesis:  H 1 : $P_{Plen0-12} \neq P_{Cort0-12}$ $P_{Plen (0-12)}$ : Increase in HRQoL score from Baseline to 6 and 12 months in Plenadrentreated patients $P_{Cort(0-12)}$ : Increase in HRQoL score from Baseline to 6 and 12 months in Cortisontreated patients	Between group comparison of longitudinal change in HRQoL score by linear mixed effect models for repeated measures.
	Secondary		
2.1	Is there a between group difference in clinical markers of cardio-metabolic health between patients receiving Plenadren and conventional thrice daily Cortisone for 12 months?	Null hypotheses: There is no difference in clinical markers of cardio-metabolic health between patients receiving Plenadren and	Comparing between-group clinical characteristics (BP, BW, BWC, BMI), lipids, glucose and HOMA index between Plenadren-treated and Cortison-treated patients.

© 2015-2021 TransCelerate BioPharma

Doc. No. CT 2.01.01. Valid from 31 Jan 2022.

Only the electronic version is valid.

Page 42 of 65

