#### 9.2.1. General Considerations

Descriptive statistics will be presented with number and percentages for categorical variables and means and standard deviation for continuous variables. In case of clearly skewed continuous variables, they will be presented with median and interquartile range (25th and 75th percentiles). Demographics and baseline characteristics will be presented with descriptive statistics without any hypothesis testing. Continuous variables will be analyzed by t-tests, linear regression, mixed models or appropriate non-parametric alternatives. To investigate a treatment-by-time effect on relevant variables, we will use the likelihood ratio test by comparing the log-likelihood between models with and without the treatment-by-time term. To obtain P for trend in means within treatment groups, the effect of time will be included as a linear term in the mixed effect model, using the z test. To obtain P for model-predicted mean difference between treatment groups for different visit time, we will perform a post-hoc test for pairwise comparison (z test).

If missing data is regarded as having a significant effect on the conclusions of the trial, sensitivity analyses with different methods for handling missing data will be included. Such methods may include complete case analyses, worst case/best case imputation and multiple imputation techniques.

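### Section 9 sets two deadlines for finalising the SAP, and in this open-label trial the later one would let choices the protocol leaves open be fixed after most 12-month HRQoL data exist

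*Protocol*

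**What the plan says.** The deadline for the SAP appears twice in the protocol's statistics section, in two nearly identical paragraphs.

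- Opening paragraph of Section 9 (before 9.1): "The statistical analysis plan will be finalized prior to inclusion of the first participant".
- Section 9.2: "The statistical analysis plan (SAP) will be finalized prior to end of trial".

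Section 4.1 fixes the end point: "The end of the study is defined as the date of the last visit of the last participant in the study". Section 10.1.9 gives the same definition.

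On blinding, Section 6.4 says: "This is an open-label study; potential bias will be reduced by central randomization". On the primary outcome, Section 8.2.1 says: "Two HRQoL will be sampled at baseline and after 1, 6 and 12 months". For the primary objective, Section 9.1 names the method: "Between group comparison of longitudinal change in HRQoL score by linear mixed effect models for repeated measures".

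**The concern.** A protocol may leave detail to the SAP. What then matters is when that detail is locked, and here the protocol gives two answers. In a blinded trial a late SAP does less harm, because the accumulating data cannot be read by arm. This trial has no blind, the primary outcome is self-reported, and the protocol does not say who may see outcome data by arm before the SAP is signed. A team relying on Section 9.2 alone could finalise the SAP near the end of follow-up and believe it had complied, while breaching the opening of Section 9. The choices still open at that stage bear on the primary conclusion.

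**Working it through.** No printed figure depends on the SAP date, and the sample size does not change with it. The check sets the passages side by side, then asks how much data could exist and what is still open.

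**1. The two deadlines.** I read end of trial in 9.2 as end of study in 4.1 and 10.1.9.

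| Place | SAP final before | Participants with 12-month HRQoL by then |
|---|---|---|
| Section 9, opening | first inclusion | 0 |
| Section 9.2 | last participant's last visit | up to nearly all |

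**2. How much data could exist at the later limit.** Inputs: 50 participants (Section 1.1), 12 months of treatment (Section 1.1), 10% drop-out (Section 9.3). Follow-up has a fixed length, so participants who entered earlier are due at month 12 before the last one.

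- Due at month 12 before the last visit: at most 50 − 1 = 49.
- With 10% drop-out: 49 × 0.9 = 44.1, about 44 of 50.

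This is the upper end, for sign-off just before the last visit. The protocol gives no accrual timetable, so the count at an earlier sign-off cannot be derived.

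**3. What the protocol fixes and what it leaves open.**

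- Fixed: the model class for the primary objective (Section 9.1).
- Open, instrument: Section 3 puts both AddiQoL-30 and RAND-36 in the primary endpoint and does not say which decides. Section 9.3 powers the trial on AddiQoL only.
- Open, time point: Section 9.1 names 6 and 12 months; Section 3 also lists 1 month.
- Open, missing data: Section 9.2.1 makes further analyses conditional, "If missing data is regarded as having a significant effect on the conclusions of the trial, sensitivity analyses", and lists several possible methods.
- Section 9.1.1 gives multiplicity adjustment as not applicable.

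**4. Illustration only.** Suppose the more favourable result were picked after seeing the data, each tested at two-sided 0.05. With independent results the type I error is 1 − 0.95^m:

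- m = 2 (two instruments): 1 − 0.95² = 0.0975.
- m = 4 (two instruments at two time points): 1 − 0.95⁴ = 0.185.

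Simulation with equally correlated normal statistics, at correlations from 0.9 down to 0.3, gives 0.071 to 0.095 for m = 2 and 0.092 to 0.174 for m = 4. The documents give no correlation and no sign that such picking is intended. These figures show why the lock date matters; they do not estimate a bias in this trial.

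**The case against.** The two sentences are not mutually exclusive: an SAP finalised before the first inclusion satisfies both. The SAP and its date are not shown, so the earlier rule may have been met. Section 9.2 describes the SAP as a more detailed account of analyses already outlined, and Section 9.1 already names the primary model. Section 9.2 also schedules the main analysis only after all participants have finished and the data are validated, and no interim analysis is described. All of this stands and limits the consequence. It does not remove the conflict, because the protocol still permits the later date and the deciding instrument and time point are still open.

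A reader might infer more than the documents support:

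- **That investigators watch HRQoL accumulate by arm.** Patients complete the questionnaires and staff complete a separate form. No section says that staff review HRQoL scores, still less pooled by arm. Knowing one patient's allocation is not the same as seeing arm-level results.
- **That the whole analysis could be chosen late.** The named mixed model rules that out for the primary objective.
- **That 49 of 50 (98%) would have complete 12-month data.** That is the worst case for timing and ignores the assumed drop-out.
- **That sites could finalise the SAP late.** The protocol gives sites no role in finalising it.
- **That Section 6.4 or the conditional missing-data rule is itself the fault here.** Central randomisation is offered there only as reducing bias, and how sensitivity analyses are triggered is a separate question. They matter here only because they show that there is no blind and that a choice is still open.

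**Conclusion.** The point holds in a limited form. Current text sets two deadlines for the same document, at opposite ends of the trial. The later one would allow the deciding instrument, the deciding time point and the missing-data methods to be fixed when up to about 44 of 50 participants could have 12-month HRQoL data, against none under the earlier one. That count assumes sign-off just before the last visit, 50 participants and 10% drop-out. The finding concerns what Section 9.2 permits. The documents do not show that anyone looked at data by arm or that the SAP was late, and the bias cannot be sized from them. Because the trial is open-label, this is more than a clerical mismatch and should be corrected.

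**What to change.** In Section 9.2, delete the end-of-trial deadline so that one rule remains: the SAP is finalised before the first participant is included, as the opening of Section 9 already says. If inclusion has already begun, state the actual SAP date and require sign-off before any HRQoL outcome is summarised by arm.

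The cost is that the SAP must be written earlier and the protocol amended; Section 10.1.1 requires ethics committee approval for amendments. Visits, treatment and sample size do not change.

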#### 9.2.1. General Considerations

Descriptive statistics will be presented with number and percentages for categorical variables and means and standard deviation for continuous variables. In case of clearly skewed continuous variables, they will be presented with median and interquartile range (25th and 75th percentiles). Demographics and baseline characteristics will be presented with descriptive statistics without any hypothesis testing. Continuous variables will be analyzed by t-tests, linear regression, mixed models or appropriate non-parametric alternatives. To investigate a treatment-by-time effect on relevant variables, we will use the likelihood ratio test by comparing the log-likelihood between models with and without the treatment-by-time term. To obtain P for trend in means within treatment groups, the effect of time will be included as a linear term in the mixed effect model, using the z test. To obtain P for model-predicted mean difference between treatment groups for different visit time, we will perform a post-hoc test for pairwise comparison (z test).

If missing data is regarded as having a significant effect on the conclusions of the trial, sensitivity analyses with different methods for handling missing data will be included. Such methods may include complete case analyses, worst case/best case imputation and multiple imputation techniques.

## 9.2.2. Primary Endpoint Analysis

All the primary, secondary and explorative endpoints are defined in section 3.

If missing data is regarded as having a significant effect on the conclusions of the trial, sensitivity analyses with different methods for handling missing data will be included. Such methods may include complete case analyses, worst case/best case imputation and multiple imputation techniques.

#### **9.2.2.1. Definition of endpoint(s)**

All the primary, secondary and explorative endpoints are defined in section 3.

If missing data is regarded as having a significant effect on the conclusions of the trial, sensitivity analyses with different methods for handling missing data will be included.

© 2015-2021 TransCelerate BioPharma

Doc. No. CT 2.01.01. Valid from 31 Jan 2022. Only the electronic version is valid.

Page 45 of 65

Such methods may include complete case analyses, worst case/best case imputation and multiple imputation techniques.

## 10. Supporting Documentation and Operational Considerations

# 10.1. Appendix 1: Regulatory, Ethical, and Study Oversight Considerations

The study will be performed in accordance with the protocol, the World Medical Association Revised Declaration of Helsinki (2008), the ICH Harmonized Tripartite Guideline for Good Clinical Practice, and any local regulations. The Ethics committee for medical research, Western Norway has granted permission to conduct the trial (ADNorGC). The patient will receive oral and written information concerning the study.

ROAS have ethical approval (REK 2013/1504) and is licensed by the Norwegian Data Protection Authority (1). This specific project was submitted to IEC in mid-2021, and an ethical approval has been obtained. Likewise, the project will be registered in the ClinicalTrials.gov database prior to study start.

All participants will receive thorough oral and written information before providing written consent for study participation. The participants are free to withdraw their consent at any time during the study. Clinical records and results will be archived in hospital records. Data will be collected to computerized research files without patient identifiers and stored according to the hospitals' research ethics guidelines. Biological research materials (blood samples) are coded and stored at laboratory at Haukeland University Hospital according to general regulations, D

Patients will be instructed to report any adverse events during the study period to the recruiting physician. If a patient develops conditions meeting the exclusion criteria or serious adverse events, the patient will be withdrawn from the study. The recruiting physician may also discontinue study participation at any time if it is considered necessary for any of the following reasons:

- Significant protocol deviation or violation.
- Significant failure to comply with study requirements.

Deviation log: We encourage doctors in charge of patients to report all deviations in the protocol to the coordinating investigator or medical monitor, as well as to register in the patient journal.

The study documentation and research data will be stored 5 years after the termination of the study. [name] will be responsible for this repository. After the termination of the study, the Regional Committee for medical and health research ethics will be notified. If needed to terminate the study earlier, we will notify the Regional Committee for medical and health research ethics within 15 days and the reason of the premature termination will be clarified.

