### 6.8.1. Rescue Medicine

The study site will not supply any form of study specific rescue medication. However, participants will be prescribed hydrocortisone for intramuscular use as per standard care, for use in case of an adrenal crisis. Occurrence of adrenal crisis will be documented at each study visit in the study-specific form. An adrenal crisis leading to admission will be registered as a SAE.

© 2015-2021 TransCelerate BioPharma

Doc. No. CT 2.01.01. Valid from 31 Jan 2022. Only the electronic version is valid.

Page 27 of 65

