# 7.2. Participant Discontinuation/Withdrawal from the Study

- A participant may withdraw from the study at any time at the participant's own request for any reason (or without providing any reason).
- A participant may be withdrawn at any time at the discretion of the investigator for safety reasons.
- At the time of discontinuing from the study, if possible, an early discontinuation visit should be conducted, as shown in the SoA. See SoA for data to be collected at the time of study discontinuation and follow-up and for any further evaluations that need to be completed.
- The participant will be permanently discontinued from the study intervention and the study at that time.
- If the participant withdraws consent for disclosure of future information, the sponsor may retain and continue to use any data collected before such a withdrawal of consent.
- If a participant withdraws from the study, the participant may request destruction of any samples taken and not tested, and the investigator must document this in the site study records.

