## 8.4.1. Time Period and Frequency for Collecting AE and SAE Information

All SAEs and AEs will be collected from the start of study intervention until visit 6 at the time points specified in the SoA (Section 1.3).

All SAEs will be recorded and reported to the sponsor or designee immediately and under no circumstance should this exceed 24 hours, as indicated in Appendix [3/7]. The investigator will submit any **updated SAE data to the sponsor within 24 hours** of it being available.

Investigators are not obligated to actively seek information on AEs or SAEs after conclusion of the study participation. However, if the investigator learns of any SAE, including a death, at any time after a participant has been discharged from the study, and the investigator considers the

© 2015-2021 TransCelerate BioPharma

Doc. No. CT 2.01.01. Valid from 31 Jan 2022.

Only the electronic version is valid.

Page 39 of 65

event to be reasonably related to the study intervention or study participation, the investigator must promptly notify the sponsor.

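### Appendix 1 requires withdrawal from the study after any SAE or emergent exclusion condition; for SAEs this conflicts with section 7.2, and following it ends scheduled HRQoL, crisis and new-SAE collection

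*Protocol*

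**What the plan says.** Appendix 1 (Protocol 10.1) gives a rule without exceptions: "If a patient develops conditions meeting the exclusion criteria or serious adverse events, the patient will be withdrawn from the study". The sentence after it lists further grounds, such as protocol deviation or non-compliance, on which the recruiting physician *may* stop participation.

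Section 7.2 is the operative withdrawal section. It says "A participant may be withdrawn at any time at the discretion of the investigator for safety reasons". On the effect of withdrawal it says "The participant will be permanently discontinued from the study intervention and the study at that time", and on the last contact, "At the time of discontinuing from the study, if possible, an early discontinuation visit should be conducted, as shown in the SoA".

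The data at stake are set out elsewhere:

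- Primary endpoint (8.2.1): "Two HRQoL will be sampled at baseline and after 1, 6 and 12 months".
- Crises (6.8.1): "Occurrence of adrenal crisis will be documented at each study visit in the study-specific form", and "An adrenal crisis leading to admission will be registered as a SAE".
- Events after participation ends (8.4.1): "Investigators are not obligated to actively seek information on AEs or SAEs after conclusion of the study participation".

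Section 3 lists adverse events, SAEs and adrenal crises among the outcomes compared between arms.

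**The concern.** A rule that removes a patient from the study because of a post-randomisation event decides which data will exist. Here the trigger is an event that plausibly affects quality of life, and in the case of an admitted adrenal crisis it is itself a study outcome. If the rule is applied, HRQoL is missing selectively after such events. A patient's first admitted crisis also ends systematic observation of any later ones. No analysis can recover follow-up that was not collected.

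The protocol also gives sites no single instruction. For an SAE, Appendix 1 orders withdrawal and 7.2 leaves it to judgement. Sites may therefore act differently, and in an open-label trial the investigator knows the arm when deciding which text to follow.

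**Working it through.** **1. Is the Appendix 1 rule mandatory?** Yes. It uses *will*, and the next sentence introduces separate optional grounds with *may also*. It therefore cannot be read as loose wording for a permission.

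**2. What triggers it?** Any SAE, related to study drug or not, because the definitions in 10.2.1 and 10.2.2 do not require causality. Inpatient admission for an untoward event qualifies, and 6.8.1 names admission for adrenal crisis. Elective admission for an unworsened pre-existing condition (10.2.2) and social admission (10.2.1) do not qualify.

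**3. Where is the conflict?**

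| Event | Appendix 1 | Section 7.2 | Safety sections |
|---|---|---|---|
| SAE | withdraw | investigator's discretion | 8.4 lists serious events separately from events that caused discontinuation; 8.4.1 collects SAEs to visit 6; 8.4.3 follows the patient at later visits or contacts |
| Emergent exclusion condition | withdraw | not addressed | pregnancy only: 8.3.4 and 8.4.5 |

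The conflict with 7.2 is therefore confined to SAEs.

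**4. What does withdrawal stop?** By 7.2 the patient leaves both drug and study. The remaining HRQoL assessments (8.2.1) and visit-based crisis recording (6.8.1) then stop, and 8.4.1 removes any duty to look for new SAEs.

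**5. What remains?** Index SAEs are followed to resolution or stabilisation (8.4.3). An early discontinuation visit is held if possible. The Schedule of Activities (1.3) marks HRQoL at baseline and visits 4, 5 and 6, with nothing at visit 7. At visit 7 it marks AE review, SAE review and the Noklus form. The protocol does not say whether the visit 7 column is the early discontinuation visit.

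**6. Post-baseline HRQoL assessments lost per withdrawn patient** (months 1, 6 and 12; assumes Appendix 1 is followed and no HRQoL is taken at exit):

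- event before month 1: 3 of 3
- between months 1 and 6: 2 of 3, which are both time points in objective 1.1 (section 9.1)
- between months 6 and 12: 1 of 3

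**7. Effect on the treatment difference.** Let p be the proportion withdrawn after an event in each arm, and d the mean HRQoL deficit of those patients relative to the rest. Leaving them out raises an arm's mean by p × d. The Plenadren-minus-Cortisone difference then shifts by p(Plen) × d(Plen) − p(Cort) × d(Cort). This is zero when both quantities are equal in the two arms, and non-zero if rates or deficits differ without offsetting. It is a simplification, because the mixed model keeps earlier scores. The protocol supplies neither p nor d, so no value can be entered.

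**8. Effect on power.** The plan's inputs (section 9.3) are SD 4, difference 4, two-sided 5% and power 90%. They give 2 × (4/4)² × (1.960 + 1.282)² = 2 × 10.51 = 21.0 per arm, in line with the stated 21. (The printed constant of 10.9 would give 21.8; this point does not depend on it.) Two-sample t power, counting completers only:

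- 25 + 25: 93.4%
- 22 + 23 (50 less the planned 10%): 90.6%
- 21 + 21: 88.5%

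Counting completers only is the worst case for a mixed model.

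**The case against.** The strongest reply is that 7.2 is a general permission. It does not mention SAEs and does not forbid a specific mandatory trigger, so the two texts could be read together. The main-body safety sections also read as if SAE patients stay, so sites may never apply one appendix sentence automatically. The first part has some force: for emergent exclusion conditions 7.2 is silent and there is no conflict with it. For SAEs the reply fails. Discretion over withdrawal for safety has little meaning if every serious safety event already compels withdrawal. That the safety sections assume otherwise confirms the inconsistency. The second part stands as a limit: every consequence above is conditional on a site following Appendix 1.

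Four stronger readings are tempting and are not supported:

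- **The primary comparison is biased by a definable amount.** The documents give no SAE rate or post-event deficit, and equal rates and deficits in the two arms give no shift.
- **The trial loses material power.** Even 42 completers of 50 leave 88.5%, and that is the worst case.
- **All follow-up stops.** Index SAEs are still followed, and an exit visit is possible.
- **HRQoL is certainly absent at exit.** The schedule marks none at visit 7, but that column is not identified as the early discontinuation visit.

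Sensitivity analyses do not remove the concern. Section 9.2.1 makes them conditional on missing data being judged to matter and only lists methods that could be used.

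**Conclusion.** The point holds as a badly fixed rule and, for SAEs, a contradiction in the current text. Followed as written, Appendix 1 ends scheduled HRQoL assessment and visit-based capture of crises and new SAEs after an event likely to be related to outcome. It costs between one and three of the three post-baseline HRQoL assessments per affected patient, on the assumption that none is taken at exit. Confidence in the textual finding is high. The effect on results cannot be quantified and may be nil, since it depends on sites applying the rule and on withdrawal rates or post-event deficits differing between arms. It should be fixed because the remedy is cheap and uncollected follow-up cannot be recovered later.

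Pregnancy is a related but separate inconsistency. Section 8.3.4 withdraws the participant from the study, and 7.2 would then end study treatment, whereas 8.4.5 keeps her on it. A reader might take this as part of the SAE conflict, but it would exist without Appendix 1.

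**What to change.** - Delete the automatic-withdrawal sentence in 10.1.
- Leave changing or stopping study drug to the investigator's discretion.
- State that an SAE or emergent exclusion condition does not by itself end follow-up, and that scheduled HRQoL, AE/SAE and crisis data are collected to month 12 unless consent is withdrawn.
- Reword 7.2 so that stopping study drug and leaving the study are separate steps.
- Separately, reconcile 8.3.4 and 8.4.5 so that one rule governs pregnancy.

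How data collected after a change of drug enter the analysis can be left to the SAP; the protocol only has to ensure that they are collected.

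The cost is a protocol amendment with ethics approval, plus health-authority approval if it is substantial (10.1.1), and reconsent if the consent form changes (10.1.3). Beyond that, a few patients who would otherwise have left attend visits that are already scheduled. Both drugs are licensed standard care and replacement is needed at all times (7.1), so continued follow-up adds no treatment risk.
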